16.1. Subject compliance

Compliance to randomised treatment will be assessed by monitoring the completion of appropriate

forms, e.g. the intra-operative radiotherapy form and the external beam radiotherapy form.

16.2. Withdrawal / dropout of subjects

The statistical analysis of the primary and secondary endpoints will be performed on an intention-to-

treat basis, which will provide an unbiased assessment of the efficacy of the intervention.

Withdrawal of Consent

Patients may "opt out" of the trial at any time. Rarely, patients may also wish to withdraw consent

for further data collection. Such cases should be reported to the TARGIT Trial Operations Office so

that no further data are entered onto the database, as specified in the patient information leaflet and

appropriate Standard Operating procedure. Data captured before consent was withdrawn will be used

in the study, but no further data, beyond this date will be collected or used in any analysis.

The TSC and in particular the DMC will monitor compliance and withdrawal data to determine the

effect on the power of the study.

TARGIT B Protocol IRAS No: 77045 Version 6.0, Dated 10/09/2018

Page 37 of 46

17. Interim analysis and data monitoring

17.1. Stopping / discontinuation rules and breaking of randomisation code

There are no formal stopping rules in this trial. The TSC (with or without the recommendation of the

DMC) may decide to stop the trial prematurely, particularly if there are unforseen safety issues.

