15.1. Sample size calculation

In the Oxford overview of December 2005 ²⁵ of 10 BCS trials that started in 1995, patients who were node positive had a local recurrence rate of 11%. In the more recent EORTC trial, the boost arm ^{2 26-28} had a local recurrence rate for patients <41 at 5 yrs of 9.5% and at 10 years of 13.5% and for patients 41-50, 8.7% at 10 years. Although the overall 10-year local recurrence rate was 6.2%, the recurrences were "concentrated" in the younger patients. Furthermore, the trial population was at low risk of recurrence- most tumours were <2cm and 91.9% were node negative. On the other hand, the TARGIT-B trial will focus on patients aged 45 or less, or with adverse features. Considering that local recurrence rates are reducing substantially with modern systemic therapy, we have estimated that the local recurrence rate in the conventional arm will be 5.64%.

[figure not shown]
In the long term results of our pilot series of 299 patients which received the proposed experimental treatment had even higher risk tumours (29% node positive vs. 20% node positive in the overview), but had the actuarial 5 year local recurrence rate of 1.73% ¹¹ ¹², which was about half of the expected recurrence rate in this unselected group of patients. In women <50, this study had a local recurrence of 2.1% (SE 1.5). Thus we shall take the conservative estimate of 2.9% (2.1+0.5xSE=2.9%) as the expected recurrence in the experimental arm.

Therefore, the study will be powered to detect a difference between 5.64% and 2.9% (OR=0.5, exponential hazard rate of 0.80) and will need 1707 patients. (Two sided RCT with alpha=0.05 and power=80%. Assuming an attrition of 5%, we shall aim towards an accrual goal of 1796 patients, i.e., a sample size of 898 in each group.

The study is powered for a 5 year- recurrence rate. The hazard of local recurrence peaks between 2-3 years hence we have chosen the 3-year time point for the interim analysis. An interim analysis will be performed at a median follow up of 3 years, or after 41 events, whichever is earlier. At this point may revise the sample size by considering both efficacy and futility analysis. The DMC will of course regularly review the data for both safety and efficacy as per MRC guidelines.

Using Lan-DeMets Alpha spending function with O'Brien-Fleming Boundary to reject null hypothesis.

Cumulative Patient Accrual	Alpha Spent			
~1000 (41 events)	0.003			
1796	0.035			

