15.2. Statistical analysis

Planned Statistical Analysis: The primary endpoint is the incidence of local recurrence. All comparison will be done on an "intent to treat" basis where all randomised patients will be included in the statistical analysis. Between-treatment group comparisons of proportion of local recurrence will be compared using simple Chi-squared test. Kaplan-Meier curves and log-rank test will be used to compare the time to local recurrence in the two treatment arms. Proportional Hazard regression models will control for possible confounding variables when comparing local recurrence in the treatment groups. We will report 95% confidence intervals for all reported proportions and hazard ratios.

Interim Analysis: Interim analyses will be carried out when 41 events occur or at a median follow up of 3 years, whichever is earlier. We have chosen 3 years because it will include the peak of hazard of local recurrence. This analysis will include the assessment for the need to change the sample size, as well as futility analysis about the continuation of the trial.

In addition, analysis of data will be carried out regularly by the DMC as per MRC guidelines.

Handling of loss to follow up or missing data: In order to carry out an Intent To Treat (ITT) analysis and avoid potential bias resulting from missing data, multiple imputation methods will be used after the missingness mechanisms are established. A full report of the patterns of missing data will be reported based on the recent CONSORT guidelines²⁹. Sensitivity analysis will be carried out and reported.

Planned subgroup analyses: This will include immediate vs. delayed boost (as a second procedure), pre- vs post- menopausal chemotherapy vs. no chemotherapy, neo-adjuvant vs. other, ER, PgR, HER2 status, Oncotype DX score. Further factors will be decided before unblinding of the data.

16. Compliance and withdrawal

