The main ethical issue is the necessity of an additional procedure that would be required in those

patients who are found to be suitable for the trial after their primary operation has already been

performed, and who would otherwise not need a second operation. These patients would be at much

higher risk of local recurrence even after routine radiotherapy (about 15-20%) and thus could

potentially derive significant benefit from TARGIT-boost. The consenting physician/surgeon will

carry out careful discussions about the risk of a second operation (which may not be significant in

these patients who would usually be young and fit) vs. the possibility of a superior result and decision

TARGIT B Protocol IRAS No: 77045 to enrol will be taken on an individual patient basis. We expect that these will constitute about 90 to

120 cases out of the total accrual of 1796.

Research Governance

The sponsor for this clinical trial is UCL. The overall research governance of the trial is determined

largely by the sponsor, including Standard Operating Procedures and Data Protection.

Each centre takes responsibility for the collection and management of its own data. Randomisation

is performed centrally though the TARGIT Trial Operations Office based in London which is also

responsible for the administration of the trial database. Access to the entire dataset is restricted to

designated trials staff and the Trial Statistician. Regular electronic reports will be produced and

passed to each centre for audit and checking purposes. This not only allows each centre to have full

responsibility for its own data, but also ensures there is adequate backup and central auditing of the

data. Standard operating procedures are in place for any data management or clinical queries.

The project is managed by a 4-tiered approach: quarterly meetings of the Trial Steering Committee;

biannual meetings of the Data Monitoring Committee; monthly meetings of the Trial Operations

Group; and weekly meetings of operational staff in the Trial Operations Office. The Trial Operations

Group is responsible for the project management and consists of seven members who are all co-

applicants of this grant. The Trial Steering Committee's role will be overarching as they are the

custodian of the data. The Trial Operations Office is based at UCL and the finances are managed by

the University finance office, which ensures propriety.

Data Monitoring Committee (DMC)

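### Section 17.1 denies any formal stopping rule while section 15.1 sets a formal efficacy boundary, and the DMC efficacy reviews and the effect-based resizing are tied to no alpha, so type I error control is not secured

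*Protocol*

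**What the plan says.** Four elements of the protocol bear on when an efficacy claim can be made.

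- **A boundary exists (15.1).** The plan specifies "Using Lan-DeMets Alpha spending function with" an O'Brien-Fleming boundary whose stated purpose is rejection of the null hypothesis. The table has two rows: alpha 0.003 at about 1000 patients (41 events) and 0.035 at 1796 patients. The interim falls at 41 events or at a median follow-up of 3 years, whichever comes first.
- **No rule exists (17.1).** "There are no formal stopping rules in this trial". The TSC may stop early with or without DMC advice. Safety is named as a particular reason, not the only one.
- **More efficacy reviews (15.1, 15.2).** Section 15.1 has the DMC review both safety and efficacy regularly. Section 15.2 says "In addition, analysis of data will be carried out regularly by the DMC as per MRC guidelines". Section 18 gives two meeting frequencies: "biannual meetings of the Data Monitoring Committee" under Research Governance, but probably annual meetings for the first two years under Data Monitoring Committee.
- **The size may change on efficacy (15.1).** "At this point may revise the sample size by considering both efficacy and futility analysis". No method, cap or adjusted final test is attached.

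**The concern.** A spending function protects the error rate only if each look that could lead to an efficacy claim spends from it and the final test uses what remains. Here alpha is given to one interim and the final analysis, other efficacy reviews are expected, and the section on stopping says that nothing formal applies. A DMC whose data crossed the 15.1 boundary would find one section treating this as grounds to reject the null hypothesis and another saying that no rule exists.

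The resizing provision is a separate route. An ordinary group-sequential boundary does not protect a conventional final test when the final size was chosen from the observed treatment effect.

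At stake is whether a superiority claim on the primary endpoint, after an early stop or a resized trial, has a known false-positive rate.

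**Working it through.** **Inputs (15.1).** "Two sided RCT with alpha=0.05 and power=80" per cent; "powered to detect a difference between 5.64% and 2.9" per cent; 1707 patients; "Assuming an attrition of 5%, we shall aim towards an accrual goal of 1796 patients"; alpha 0.003 and 0.035; interim at 41 events.

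**1. The plan's sample size reproduces.** Per arm, with mean proportion 0.0427:

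n = [1.960·√(2 × 0.0427 × 0.9573) + 0.842·√(0.0564 × 0.9436 + 0.029 × 0.971)]² / 0.0274²
= (0.5604 + 0.2401)² / 0.000751 ≈ 853.5, or 1707 in total.

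Then 1707/0.95 = 1796.8, against 1796 stated. The size was therefore computed at a final two-sided level of 0.05.

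**2. The alpha table reproduces only in part.** The two-sided O'Brien-Fleming-type spending function at 0.05 is α(t) = 4 − 4Φ(2.241/√t).

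- Expected five-year events are 1707 × 0.0427 = 72.9, or 1796 × 0.0427 = 76.7. So 41 events is t = 0.56 or 0.53.
- α(0.50) = 0.0031, α(0.53) = 0.0043 and α(0.56) = 0.0056. The printed 0.003 matches t = 0.50.
- Cumulative alpha at t = 1 is 0.05. The final nominal level is 0.0490 (interim at t = 0.50) or 0.0482 (t = 0.56). The printed 0.035 is neither.

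**3. Two planned looks, printed levels binding.** Take Z₁ and Z₂ as bivariate normal with correlation √t, and limits 2.968 (0.003) and 2.108 (0.035). The probability under the null that either is exceeded is 0.0362 at t = 0.50 and 0.0360 at t = 0.56. Read as increments, the levels sum to 0.038.

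**4. Additional DMC looks (simulated under the null).** The protocol fixes neither their number nor a threshold. I assumed 8 or 15 looks, spaced equally in information or in calendar time. The calendar version uses 250 patients a year and the plan's hazards, which reach about 73 events near 8.4 years.

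| Rule at each extra look / final | 8 looks | 15 looks |
|---|---|---|
| 0.003 / 0.035, equal spacing | 4.2% | about 4.6% |
| 0.003 / 0.035, calendar spacing | 4.6% | 5.3% |
| 0.01 / 0.049, calendar spacing | 8.4% | 10.4% |
| 0.05 / 0.05, equal spacing | 18% | 23% |
| 0.05 / 0.05, calendar spacing | 22% | 30% |

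**5. Effect-based sample-size revision (simulated).** Assumed rule: at t = 0.56, increase to reach 80% conditional power under the observed trend, with interim level 0.003 and a conventional final test.

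| Final level | Cap 1.5× | Cap 3× | Cap 4× |
|---|---|---|---|
| 0.035 | 4.1% | 4.8% | just under 5% |
| 0.049 | 5.7% | 6.6% | 6.8% |

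If decreases are also allowed, the figures are about 5% to 6% with a final 0.035 and about 6.6% to 7.7% with 0.049, depending on the rule and cap.

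**The case against.** The best reply is that the printed levels are conservative. Used as written, they cost about 3.6% at the planned looks. Even with many further looks at 0.003, or an effect-based increase, the error stays under 5% in most scenarios and barely exceeds it in the worst of these (5.3%). Treating an efficacy boundary as advisory does not itself inflate type I error. The DMC's remit is said to be agreed, its reviews are tied to MRC guidelines that are not reproduced, and a SAP or charter may hold the thresholds and the resizing method. No passage makes each DMC meeting a hypothesis test, and permission to revise the size does not specify an uncorrected final test.

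Most of this stands. A reader might infer from sections 15 and 17.1 that type I error is uncontrolled, or that its true rate is 20% or more. The documents do not support that: the high figures need a stopping threshold of p<0.05 at every review, which no section states.

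What the reply does not remove is the contradiction. Its reassurance depends on 0.003 and 0.035 binding, and section 17.1 says that no formal rule binds. A charter or SAP would still sit beneath a protocol that says both things.

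**Conclusion.** Wrong as written. Sections 15.1, 15.2 and 17.1 cannot all stand, and the DMC meeting frequency in section 18 is also inconsistent. Type I error control is not secured; it is not shown to be lost.

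The size depends on which section prevails:

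- **Printed levels bind:** about 3.6% at the two planned looks; 4.2% to 4.6% with 8 to 15 equally spaced looks (up to 5.3% with 15 calendar-spaced looks); 4.1% to 4.9% after an effect-based increase.
- **Printed levels do not bind, as 17.1 implies:** about 5.7% to 6.8% after an effect-based increase with a final test near 0.049. As a worst case only, 18% to 30% if every review could stop the trial at p<0.05.

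The number and spacing of looks, their thresholds, and the resizing rule and cap are assumptions. The contradiction and the failure of 0.035 to follow from the named function do not depend on them.

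**What to change.** 1. **Recompute the 15.1 table before making it govern.** At two-sided 0.05 with two looks, the named function gives 0.003 at information 0.50 or 0.0056 at 0.56, cumulative 0.05, and a final nominal level of about 0.048 to 0.049. State the information fraction as events observed over events planned, because the whichever-is-earlier trigger leaves it open. If 0.035 is intended, say why: at 1707 patients a 0.035 test has about 76% power.
2. **Replace the first sentence of 17.1.** State that the 15.1 spending boundary governs any efficacy claim from an early stop, that futility is non-binding, and that the existing freedom of the TSC and DMC to stop for safety is unchanged.
3. **Amend 15.1 and 15.2** to say that other DMC reviews are not a basis for an efficacy stop unless they spend alpha from the same function at their event fraction. Align the two meeting frequencies in section 18.
4. **Resizing:** base it on the blinded pooled event rate or, if it uses the observed effect, name a weighted combination test for the final analysis.

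The cost is wording in the protocol and DMC charter, settled before the interim. Patient numbers barely move: a final level of 0.049 needs 1718 patients before attrition, against 1708 at 0.05 with whole patients per arm. The downside is that informal efficacy looks are given up.

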17.2. Monitoring, quality control and assurance

Essential data will be verified using manual and electronic validation checks. The validation is carried

out at and/or after completion of data entry of each case record form (CRF). Any missing or

ambiguous data will be queried with site staff.

Quality Assurance

Quality assurance (QA) in radiotherapy is defined as "[the set of] procedures that ensures consistency

of the medical prescription and the safe fulfilment of that prescription as regards dose to the target

volume, together with minimal dose to normal tissue, minimal exposure to personnel, and adequate

patient monitoring aimed at determining the end result of treatment" ³⁰. In the UK the Department of

Health issues a mandatory standard. It is based on a formal quality management system issued by the

International Standards Organisation ³¹. This is a multidisciplinary responsibility to ensure

consistency in absolute dosimetry, dose delivery, volume definition and reproducibility are

paramount in radiotherapy QA and have become even more important with the advent of conformal

therapy. Formal procedures should ensure that every "non-conformity" (i.e., a failure of any element

of the system or its procedures) is identified and controlled, and that corrective action is taken to deal

with the underlying causes. The quality system itself must be formally audited at regular intervals to

ascertain whether it is working as intended. We expect that all investigators joining the TARGIT trial

will be working to local or national standards which conform to the international guidelines. The Trial

Steering Committee therefore is content that no additional quality assurance exercise is necessary for

conventional external beam radiotherapy provided that the investigators at each site are subject to

local/national guidelines similar to those quoted above. If no such scheme operates at an investigator

site the principle investigator must inform the TARGIT Operations Office who will inform the Trial

Steering Committee to determine an appropriate course of action.

Quality assurance for the Intrabeam

All the evidence to date supports the description of the Intrabeam as delivering an accurate and

reliable dose. The local physics departments are responsible for verifying the miniature X-ray source

is operational prior to use, and setting up the parameters within the control console software for

Page 38 of 46

treatment delivery. During the procedure, the control console monitors the system for safe and

accurate dose delivery.

The Intrabeam System includes a full set of quality assurance tools. These, combined with the

operator interface of the control console allow complete verification of all of the performance

functions in minutes and constant monitoring of critical treatment parameters throughout the

treatment period. The sites are responsible for QA according to the manufacturer's instructions and

these data should be made available to the trial centre. Recalibration of the output of the X-Ray Source

must be performed at least annually and a report this needs to be sent to the trial centre. Carl Zeiss

offers contracts for annual manufacturer service. We strongly recommend all centres to use this

service.

Parameters to be collected for QA Audit

For each trial treatment delivered the following will be collected: Applicator diameter, prescribed

dose (should usually be the same in each case) and treatment time.

17.3. Assessment of safety

Data on safety will be gathered by the following methods:

• From serious adverse event forms.

• From the protocol violation/deviation form.

• From the complication forms.

• From data missing or contained within other CRFs.

Procedures for dealing with the above are contained in relevant Standard Operating Procedures.

TARGIT B Protocol IRAS No: 77045 Version 6.0, Dated 10/09/2018

Page 39 of 46

18. Ethical considerations

Risks and benefits

The mature pilot study has confirmed that it is safe and feasible to give intraoperative radiotherapy

with the TARGIT technique ^{32 33}. There is no significant acute toxicity as long as attention is paid to

the meticulous surgical approach. For example, the skin needs to be at least one cm away from the

applicator and protected from the radiation so that there is no delay in wound healing. We have also

demonstrated that this technique can be adopted in over 30 worldwide centres safely. We have a

robust training and auditing programme that each centre needs to pass before they start recruiting

patients in the trial.

The risk of long term toxicity will be assessed carefully. This is mainly in the form of normal tissue

reactions such as fibrosis in the tissue receiving the higher dose of radiotherapy. Our clinical

experience suggests that this risk is low, and does not appear to be more than conventional treatment.

This is not surprising as the volume of tissue receiving the high dose with the TARGIT technique is

small, compared to other methods of radiotherapy. Long term results of the phase 2 study (maximum

follow up 121 months) 32 33 have also borne out the safety of the technique. A German cohort of

patients has also confirmed the long-term safety of the technique ³⁴.

Informing potential trial participants of possible benefits and known risks

Suitable patients will be identified at multi-disciplinary team meetings and approached by a member

of the clinical team (usually the breast surgeon). Patients will be informed of the trial and given an

information leaflet to take home and discuss with members of their family. Randomisation would

take place only after written informed consent has been obtained.

UK ethics approval for this study has already been granted (Main REC 06/S1401/108 Oct 2006).

The Intrabeam device has FDA approval and a CE mark, and in this study, is being used for the

purposes for which the approval was given.

The main ethical issue is the necessity of an additional procedure that would be required in those

patients who are found to be suitable for the trial after their primary operation has already been

performed, and who would otherwise not need a second operation. These patients would be at much

higher risk of local recurrence even after routine radiotherapy (about 15-20%) and thus could

potentially derive significant benefit from TARGIT-boost. The consenting physician/surgeon will

carry out careful discussions about the risk of a second operation (which may not be significant in

these patients who would usually be young and fit) vs. the possibility of a superior result and decision

TARGIT B Protocol IRAS No: 77045 to enrol will be taken on an individual patient basis. We expect that these will constitute about 90 to

120 cases out of the total accrual of 1796.

Research Governance

The sponsor for this clinical trial is UCL. The overall research governance of the trial is determined

largely by the sponsor, including Standard Operating Procedures and Data Protection.

Each centre takes responsibility for the collection and management of its own data. Randomisation

is performed centrally though the TARGIT Trial Operations Office based in London which is also

responsible for the administration of the trial database. Access to the entire dataset is restricted to

designated trials staff and the Trial Statistician. Regular electronic reports will be produced and

passed to each centre for audit and checking purposes. This not only allows each centre to have full

responsibility for its own data, but also ensures there is adequate backup and central auditing of the

data. Standard operating procedures are in place for any data management or clinical queries.

The project is managed by a 4-tiered approach: quarterly meetings of the Trial Steering Committee;

biannual meetings of the Data Monitoring Committee; monthly meetings of the Trial Operations

Group; and weekly meetings of operational staff in the Trial Operations Office. The Trial Operations

Group is responsible for the project management and consists of seven members who are all co-

applicants of this grant. The Trial Steering Committee's role will be overarching as they are the

custodian of the data. The Trial Operations Office is based at UCL and the finances are managed by

the University finance office, which ensures propriety.

Data Monitoring Committee (DMC)

An independent DMC has been appointed and their remit agreed. They will regularly review the data

collected during the trial and report to the TSC as to whether the trial should continue and make

recommendations as to changes in the protocol.

Meetings will probably be scheduled annually for the first two years of the trial whilst accrual gains

momentum. More frequent meetings may then be held.

TARGIT B Protocol IRAS No: 77045 Version 6.0, Dated 10/09/2018

.0, Dated 10/09/2018 Page 41 of 46

19. Financing and Insurance

University College London holds insurance against claims from participants for injury caused by their participation in the clinical trial. Participants may be able to claim compensation if they can prove that UCL has been negligent. However, as this clinical trial is being carried out in a hospital, the hospital continues to have a duty of care to the participant of the clinical trial. University College London does not accept liability for any breach in the hospital's duty of care, or any negligence on the part of hospital employees. This applies whether the hospital is an NHS Trust or otherwise.

Participants may also be able to claim compensation for injury caused by participation in this clinical trial without the need to prove negligence on the part of University College London or another party. Participants who sustain injury and wish to make a claim for compensation should do so in writing in the first instance to the Chief Investigator, who will pass the claim to the Sponsor's Insurers, via the Sponsor's office.

Hospitals selected to participate in this clinical trial shall provide clinical negligence insurance cover for harm caused by their employees and a copy of the relevant insurance policy or summary shall be provided to University College London, upon request.

20. Reporting and dissemination

A publication policy will be written and agreed by the Trial Steering Committee. Presentations and publications arising directly from the pre-planned analyses will be the responsibility of the Trial Steering Committee.

Other members of the medical and scientific community will be encouraged to submit requests for new analysis of the data set. However, the raw data will remain in the custodianship of the Trials Operations Group, apart from the transfer of anonymised data to the Trial Statistician for predetermined analyses.

REFERENCES

